3. Participation in a new study evaluating anti-resorptive therapy for prevention of bone loss after stopping TPTD. The new study is currently in the design phase and funding phase and precise details are not yet available

All currently enrolled subjects would be re-consented and future participants would sign a new informed consent document with the new study design.

On January 26, 2014, the Research Pharmacy informed the Principal Investigator that there was a mistake in the randomization table for the study. Subjects (n=40) should have been randomized 28:12, active Teriparatide to placebo, for 6 months, followed by a single-switchover design in which all would receive active drug. The randomization code in the table provided to the Research Pharmacy by the Study Statistician was reversed and the subjects were randomized 12:28, active Teriparatide to placebo. To date, 18 patients have been enrolled and randomized. Research Pharmacy has informed us that 12 subjects were randomized to placebo and 6 to active Teriparatide. As 12 subjects have already been randomized to receive placebo first, we will increase enrollment by one subject (total, 41) and generate an adaptive randomization table in which one of the 23 subjects yet to be enrolled will be randomly assigned to placebo and 22 will be randomly assigned to active Teriparatide. This will maintain the number of subjects treated with active drug at 28 and maintain blinding of subjects and study personnel to study assignment.

2. Study Design and Statistical Procedures

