Prior to statistical analysis, all outcome and covariate data will be summarized with descriptive statistics, outliers examined, distributions identified and normalizing transformations applied where indicated. All of the above analyses will be based upon the intention-to-treat principle. The missing data mechanism (MCAR, MAR) for all outcomes and covariates will be assessed and, in the event of a non-ignorable mechanism, analyses will subjected to the methods of Diggle and Kenward³⁹ for continuous measures or Ibrahim and Lipsitz⁴⁰ for safety outcomes. Bone turnover markers will be log-transformed prior to analysis. Inferential testing will use a 5% two-tailed type I error rate with no adjustment for multiplicity taken for primary outcome analyses. Secondary efficacy analyses type I error rates will be adjusted by Bonferroni method whereas secondary safety analyses will not. In keeping with the objective of proposed exploratory analyses to generate data patterns consistent or inconsistent with improved bone quality, no adjustment for multiplicity will be taken. No interim efficacy analyses are planned. The statistical analysis plan will be modified to account for the adaptive randomization procedure, which is relevant to Aim 1 only.

AIM 1:

Primary efficacy outcome analysis: Analysis of covariance (ANCOVA) comparison of between-group (treated vs placebo) differences in mean change in LS aBMD (g/cm^2) by DXA from pre-treated baseline to 6 months of assigned treatment with adjustment for the following continuous baseline variables LS aBMD (g/cm^2), age (years) and weight (kg).

Primary safety outcome analysis: Fisher's Exact test of between-group difference in the number of people in each assigned group reporting at least one hypercalcemia or hypercalciuria event in the first 6 months of assigned treatment; followed by Cox proportional hazards model analysis of the between-group difference in the time-to-first hypercalcemia or hypercalciuria event; followed by GEE testing of the between-group difference in the temporal pattern of the repeatedly sampled hypercalcemia or hypercalciuria events in the first 6 months of assigned treatment.

Secondary efficacy outcome analyses: TH, FN and 1/3 Radius aBMD by DXA will analyzed by ANCOVA as described for the primary outcome, above.

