Secondary safety outcome analyses: Fisher's Exact test will be used to assess treatment group differences in numbers of people endorsing each symptom reported on the symptom checklist administered at each study visit without adjustment for multiplicity. The GEE test approach proposed for the primary safety

outcome analysis of longitudinal events will be repeated for any symptom reported by >10% of either treatment group.

AIM 2:

Primary analysis: The between-group mean difference in the quad-labeled histomorphometric measured change in Mineralizing Surface (MdPm) and Bone Formation Rate (BFR/BS) at 3 months will be analyzed with ANCOVA with adjustment for the baseline continuous variables of age (years) and weight (kg.). Outcomes will be analyzed separately without adjustment for multiplicity. Secondary analyses: In the teriparatide-treated group the relationship between baseline MdPm and BFR/BS, and change in MdPm and BFR/BS in the first three months of treatment, and 12 and 24 month change in aBMD of the spine and hip by DXA and vBMD of the spine by cQCT will be assessed with multiple regression analysis. Per annum change in DXA and cQCT outcomes will be separately modeled as a function of baseline MdPm and BFR/BS, baseline level of the DXA or cQCT outcome, age, weight, bone microstructure by microCT of biopsy specimens, and change from baseline in MdPm and BFR/BS during the first three months. Other potential baseline predictors of DXA and cQCT response to teriparatide treatment will be explored with multiple regression to determine whether any clinical or constitutional measures supercede change in MdPm or BFR/BS in predicting bone change.

AIM 3:

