Visit 2 (Imaging): If the SOPEval is normal, candidates will be invited to proceed with Visit 2. Prior to initiation of any additional study procedures, an informed consent discussion will take place. Only after the informed consent (Study Consent Form) is signed will further research related procedures commence. The study will be described, including the bone biopsy procedure. Participants with fractures will be asked to bring verification (x-rays or radiology reports). They will complete standardized questionnaires to assess current diet and physical activity. We use the validated Block food frequency questionnaire (FFQ; Appendix 3)^{47,48} to assess calcium intake. Physical activity is assessed by the modified Baecke questionnaire (Appendix 4)⁴⁹⁻⁵¹. Equivocal VFA results will be evaluated with spine x-rays. Central QCT of the spine (L1 and L2) with additional single slice at L4, and HR-pQCT of the distal radius and tibia will be performed to measure volumetric BMD, body composition (subcutaneous and visceral adiposity), and cortical and Tb microstructure. Serum will be archived at -80°.At this visit, subjects will also receive tetracycline for their first round of antibiotic labeling and instructions with a scheduled dosing according to protocol. Subjects will complete labeling before the randomization visit, where they will receive Forteo and begin treatment.

52,53

Visit 3 (Randomization): During this visit, imaging results will be reviewed with the subjects. Eligible subjects who agree to participate will be randomized to TPTD or placebo (ratio 28:13) through block randomization with randomly varying block sizes of 2, 4 or 6, stratified by whether they are included on the basis of history of fractures or low BMD. Serum/urine will be archived at -80°C for batch analyses of specialized biochemistries. DNA will be obtained from peripheral blood lymphocytes for archival purposes. We will collect blood for the measurement of osteoblasts, or bone building stem cells, in the bloodstream.

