6. STUDY SUBJECTS

Inclusion Criteria:

• Premenopausal women, aged 20-48, with regular menses and no historical or biochemical secondary cause of osteoporosis; the lower age limit is to ensure epiphyses are fused, the upper to make it less likely that women will enter menopause during the study. All subjects under age 25 will be screened prior to drug administration to rule out open epiphyseal plates.

- Documented adult fractures judged to be low-trauma (trauma equivalent to a fall from a standing height or less) and/or T \leq -2.5 or Z score \leq -2.0 at the LS, FN or TH. Inclusion criteria vary slightly based on age category:
 - Premenopausal women ages 20-35 years must have at least one major osteoporotic fracture (excluding fractures of fingers, toes and face) AND low BMD defined as a T-score or Z-score ≤ -1.5 .
 - Premenopausal women above the age of 35 years should have a history of fracture AND/OR low BMD defined as Z-score < -2.0. Women above age 35 may also be enrolled on the basis on low BMD alone, without presence of prior low trauma fracture.
- Must be willing to use effective contraception throughout the period of study drug administration

Exclusion Criteria:

- History of any condition that increases the risk of osteosarcoma (Paget's disease, skeletal irradiation)
- Early follicular phase serum FSH>20 mIU/ml (to exclude perimenopausal women)
- Disorders of mineral metabolism: 1°/2° hyperparathyroidism, osteomalacia, osteogenesis imperfecta (OI) or Ehlers Danlos (ED). Subjects will not routinely undergo genetic testing for OI or ED as part of their screening evaluation. However, each subject will have a detailed medical and family history and a complete physical examination by one of the physician investigators. Women with historical features or physical examination findings suggestive of OI or ED will be referred for genetic evaluation. If the genetic evaluation is positive for OI or ED, the subject will be excluded from participation.
- Suspicion of osteomalacia (elevated alk phos, worsening bone pain with weight bearing, or bone tenderness)
- Vitamin D deficiency (serum 25-OHD[<]20 ng/ml). Women with levels of 10-20 ng/ml will be eligible after treatment with vitamin D has resulted in levels ≥20 ng/ml.
- Pregnancy within the last 3 months if there was no lactation or lactation within past 6 months
- Prolonged amenorrhea (≥ 6 months) during reproductive years (except pregnancy or lactation)

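### The Aim 1 and Aim 2 ANCOVAs omit the randomization stratum, and the plan wrongly confines the effect of the altered allocation to Aim 1

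*Combined protocol and SAP*

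**What the plan says.** **Randomization.** Section 3.A, Visit 3, gives a 28:13 ratio in "block sizes of 2, 4 or 6, stratified by whether they are included on the basis of history of fractures or low BMD".

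**Models.** Section 2.A specifies the Aim 1 primary ANCOVA "with adjustment for the following continuous baseline variables LS aBMD (g/cm^2), age (years) and weight (kg"). The Aim 1 secondary ANCOVAs (total hip, femoral neck, 1/3 radius) follow the same model. The Aim 2 primary outcomes, between-group differences in histomorphometric change at 3 months, "will be analyzed with ANCOVA with adjustment for the baseline continuous variables of age (years) and weight (kg"). No model contains the stratum.

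**Allocation in practice.** Section 1 reports that the randomization code was reversed: "Research Pharmacy has informed us that 12 subjects were randomized to placebo and 6 to active Teriparatide". For the remainder, "one of the 23 subjects yet to be enrolled will be randomly assigned to placebo and 22 will be randomly assigned to active Teriparatide".

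**Analysis response.** Section 2.A has one sentence: "The statistical analysis plan will be modified to account for the adaptive randomization procedure, which is relevant to Aim 1 only". It names no method.

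**Stratum definition.** Visit 3 does not say which level applies to a woman with both a fracture and low BMD. Section 6 requires both at ages 20-35 and allows both above 35. It adds: "Women above age 35 may also be enrolled on the basis on low BMD alone, without presence of prior low trauma fracture". At Visit 2, before randomization, "Participants with fractures will be asked to bring verification (x-rays or radiology reports".

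**The concern.** A factor used to restrict randomization normally belongs in the analysis model. If stratification has balanced the arms, omitting a prognostic stratum leaves the estimate unbiased but overstates its standard error, so the test is conservative and some power is lost.

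Here balance cannot be taken for granted. The allocation ratio was 6:12 in the first phase and 22:1 in the second, and a single placebo place among 23 women cannot be balanced over two strata. If the share of women enrolled with a fracture differed between phases, the arms would differ in stratum mix. Omission would then bias the comparison, in a direction set by which stratum gains more.

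The exposure is not limited to Aim 1. The Aim 2 primary contrast is made at 3 months, inside the placebo-controlled period, between the same arms, and its model has no BMD covariate.

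**Working it through.** **Inputs from the documents.** Section 2.B: change in LS BMD 3.7 (SD 3.3)% v 0.8 (SD 2.9)%, difference 2.9 points; correlation with baseline covariates 0.3; Aim 2 effect sizes 1.42 and 1.28. Section 2.A: two-sided 5%. Sections 1 and 2: 28:13 overall, 6:12 then 22:1.

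**Assumptions.** The documents give no stratum counts and no stratum effect. I take a partial R-squared (R2) of 0.05, 0.10 or 0.15 beyond the covariates, roughly equal strata, covariates independent of the stratum, and an unstratified 22:1 list.

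**The plan's own power figures.** At 28:12, pooled SD = sqrt((27 x 3.3^2 + 11 x 2.9^2)/38) = 3.19; residual SD = 3.19 x sqrt(1 - 0.09) = 3.04; SE = 3.04 x sqrt(1/28 + 1/12) = 1.050. Noncentral t with 35 df gives 76.6%, so the stated Aim 1 power above 90% does not reproduce. That is a separate matter and nothing here depends on it. The stated Aim 2 power above 90% does reproduce: 95.0% at 1.28 and 97.9% at 1.42.

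**Aim 1 power at 28:13.** Pooled SD = sqrt((27 x 3.3^2 + 12 x 2.9^2)/39) = 3.18; residual SD = 3.04; SE = 3.04 x sqrt(1/28 + 1/13) = 1.019. Without the stratum (36 df), power is 79.1%. With it there are 35 df and the SE is multiplied by sqrt(1 - R2).

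**Stratum mix under a 1/3 to 2/3 shift** (6 of 18, then 15 of 23 with a fracture). Expected fracture share is (2 + 22 x 15/23)/28 = 16.35/28 = 0.584 on teriparatide and (4 + 15/23)/13 = 4.65/13 = 0.358 on placebo, a difference of 0.226. The squared arm-stratum correlation is 0.226^2 x (28 x 13/41^2)/(0.512 x 0.488) = 0.044. Variance inflation is 1/(1 - 0.044) = 1.046, so the SE is multiplied by a further sqrt(1.046).

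| Aim 1 power with stratum | R2 = 0 | 0.05 | 0.10 | 0.15 |
|---|---|---|---|---|
| Strata balanced | 79.0% | 81.0% | 83.1% | 85.1% |
| 1/3 to 2/3 shift | 77.2% | 79.3% | 81.4% | 83.5% |

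**Type I error without the stratum.** 100,000 simulated null trials per setting (Monte Carlo SE about 0.07 point), three covariates, 6:12 in the first 18, then one placebo woman drawn at random from 23.

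| Fracture share, first to second phase | R2 = 0.05 | 0.10 | 0.15 |
|---|---|---|---|
| Constant | 4.6% | 4.1% | 3.6% |
| 40% to 60% | 4.8% | 4.7% | 4.4% |
| 1/3 to 2/3, first 18 balanced by stratum | 5.4% | 5.9% | 6.3% |

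With the stratum it is 4.9-5.1% throughout. The middle row is sensitive to how whole-number counts are set: a smaller check (20,000 trials per setting) fixed at 7 of 18 and 14 of 23 gave 4.9-5.2%, so read it as about 5% or below.

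**Bias under the 1/3 to 2/3 shift.** With equal strata the stratum effect is 2 x sqrt(R2) x 3.04 = 1.36, 1.92 or 2.35 points. Multiplied by 0.226, this gives 0.31, 0.43 or 0.53 points.

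**Aim 2 at 28:13, effect size 1.28.** SE = sqrt(1/28 + 1/13) = 0.336 SD. Power is 96.0% with 37 df (no stratum) and 96.0% with 36 df (stratum, balanced). With the SE inflated by sqrt(1.046) to 0.343 it is about 95%. For Aim 2 the term protects against imbalance; it does not add power.

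**The case against.** The strongest case against is that the harm rests on stacked assumptions. Type I error clearly exceeds 5% only if the fracture share roughly doubles between phases and the stratum also explains at least 5% of residual variance beyond the covariates. The documents report neither. This stands, and it limits the weight of the point.

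The existing covariates also probably carry part of the stratum. Baseline LS aBMD is in the Aim 1 model, and age is in both. Section 6 requires a fracture at ages 20-35, so low BMD alone can occur only above 35. The simulation treats covariates as independent of the stratum, so its figures probably lean high. This also stands.

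The term is not quite free either. If arm and stratum are correlated enough to cause bias, adjustment costs more than the degree of freedom: 79.1% to 77.2% at R2 = 0, with almost no gain at R2 = 0.05 (79.3%). The 0.1-point cost applies only with balanced strata.

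Finally, a stratum rebuilt from baseline data may differ from the one used in the list. That is a fair limit. It argues for a sensitivity analysis, not for leaving the factor out.

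Three stronger readings are tempting but unsupported:

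- **Type I error of 6-8%.** Simulation gives 6.0, 6.9 and 8.0% for the 1/3 to 2/3 shift if the first 18 women were also not balanced by stratum. Visit 3 says randomization was stratified, and Section 1 reports a reversed code, not lost stratification.
- **The stratum term supplies the promised SAP change.** It does not. Under an assumed 1-point drift in outcome between phases, type I error is 10.5% without the term and 10.3% with it.
- **The 22:1 list cannot be made.** Visit 3 and Section 1 are unreconciled, which does not show that the list is impossible.

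**Conclusion.** The point holds in a modest form. Two things are plain from the text: the stratification factor is missing from the Aim 1 primary and secondary ANCOVAs and from the Aim 2 primary ANCOVA, and the restriction to Aim 1 is wrong because Aim 2 compares the same randomized arms.

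The size is conditional. With balanced strata the cost of omission is a conservative test and up to about 6 points of Aim 1 power (79.1% v 85.1% at R2 = 0.15). With a large shift in mix it is a type I error of about 5.4-6.3% and a bias of 0.3-0.5 points against 2.9. With a moderate shift, type I error stays at about 5% or below. All of this rests on assumed stratum effects and on covariates independent of the stratum. A reader might infer that the trial's result is biased by the omission; without stratum counts by phase and arm, the documents do not show that. The change is worth making because it is cheap and protects against both outcomes.

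**What to change.** 1. Add the stratum as a fixed factor to the Aim 1 primary ANCOVA, the Aim 1 secondary ANCOVAs and the Aim 2 primary ANCOVA, before outcomes are analysed by arm.
2. Define it once for all 41 women from data collected before randomization, for example any qualifying low-trauma fracture versus low BMD alone. Section 6 supports this split, and it settles the women who meet both criteria.
3. Repeat the analysis with the level recorded in the randomization list, where one exists, as a sensitivity analysis. It may not exist for the last 23 women.
4. Delete the statement that the altered randomization is relevant to Aim 1 only.
5. Treat the change in allocation ratio between phases separately. The promised SAP change still needs its own content on that, for both aims.
6. As a wording point, reconcile Visit 3 with Section 1. State how the sequence was generated in each phase, the block composition, and whether the 22:1 list is stratified. An exact 28:13 ratio needs a block of 41, and 28:12 (7:3) a block of 10, so blocks of 2, 4 or 6 cannot each hold the ratio.

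**Cost.** SAP and protocol wording, no new data and one degree of freedom. If the stratum explains nothing, Aim 1 power falls by about 0.1 point with balanced strata and about 1.9 points under the 1/3 to 2/3 shift.

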randomized, double blind, placebo-controlled, single switch-over trial of TPTD in premenopausal women with IOP. Forty-one subjects will be assigned to TPTD (Group A; n=28) or placebo (Group B; n=13). At the 6 month timepoint, all subjects will receive TPTD, but blinding of original group assignment will be maintained for an additional 6 months. At the 12 month visit, the blind will be broken and those initially randomized to TPTD (Group A) will continue on study drug for an additional 12 months while those initially randomized to placebo (Group B) will continue for an additional 18 months, so that subjects in both groups complete 24 months of treatment overall. aBMD by DXA and HRpQCT will be measured at baseline and at 6 month intervals. vBMD by cQCT will be performed before randomization and after 24 months of TPTD (Table 1). A quadruple labeled transiliac crest bone biopsy will be performed at 3 months for both Group A and B. Eli Lilly & Company will provide TPTD and placebo but will supply no other funding. After 24 months of treatment in either Group A or B, all women will be offered three choices for follow up: the subjects can A) continue to to be followed for 12 months off TPTD B) choice to leave the study and be treated clinically using an anti-resorptive medication to maintain gains in bone density after treatment with TPTD, or C) join a new study to maintain gains in bone density after treatment. The new study is currently in the design phase and funding phase and precise details are not yet available.

Statistical Analysis Plan

2.A. Statistical Analysis Plan Our aims in this protocol are as follows:

Aim 1: To establish the efficacy and safety of 6 months of TPTD versus placebo in premenopausal women with IOP

Aim 2: To determine the effect of 3 months of TPTD on bone remodeling at the tissue level and the extent to which baseline and 3 month bone remodeling predicts response to TPTD in premenopausal women with IOP.

Aim 3: To determine the extent to which 12 and 24 months of TPTD improves areal and volumetric BMD, bone microarchitecture and strength (stiffness) compared to baseline measures in premenopausal women with IOP

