Subjects will be provided with calcium (citrate) caplets (Citracal + D; each 315 mg + 250 IU D) and a multivitamin (Centrum) that provides 500 IU of vitamin D daily. Most subjects will be instructed to take 2 Citracal caplets and a multivitamin; the total daily dose of calcium from supplements will be approximately 630 mg and of vitamin D 1000 IU. Subjects with very low dietary calcium intake (<500 mg/d estimated by interview and the FFQ), will be asked to take 3 Citracal caplets, while those with high dietary calcium intakes (>1,000 mg/day) will be asked to take 1 Citracal caplet.

Visits 4-5, 8-13 (Study Evaluations): At each study visit, study coordinators will assess any adverse events that transpired since the last study visit. Patients will be instructed to bring their Forteo journal and pens with them to every visit, which documents their compliance with the study medication. The purpose

of the 1-week and 1-month visits (Visits 4 & 5) is to monitor for compliance and adverse effects. At the 1-week and 1-month visit, we will also obtain fasting serum for serum calcium (safety) and at the 1-Month we will also collect serum for BTMs. These visits may be conducted on site for women who reside close to the study sites or may be a telephone contact and local blood draw for those who live at a distance. The remainder of the study visits to perform imaging studies and/or blood draws and dispense study drug are shown in Tables 1-3. We will perform a single follow-up cQCT scan after 24 months of TPTD treatment to minimize radiation exposure in these women who are of child-bearing age. At Visit 12, subjects will be presented with three options for post-TPTD follow up as described in the study design.

Visit 6 (Pre-Biopsy Clearance and Labeling): Subjects will have a pre-biopsy clearance visit with the surgeon and have safety bloods drawn and processed as per hospital regulations. Subjects will receive their second antibiotic labeling agent, demeclocycline, and accompanying labeling schedule.

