MD Visit		X	V	X	X				
Dispense TPTD		X	X X	X					
Telephone Contact [#]	X	X	X X	X	X				
Pregnancy Test BMD by DXA		X	X X	X	X				
History & Physical		X	Λ	X	X				
Adverse Events	v	X	Х	X	X				
Serum FSH	X	X	Λ	X	X				
HR-pQCT		x		X	X				
Central QCT		Λ		X X	Λ				
VFA by DXA		x		X	x				
		X	X	X	X				
Calciotropic Hormones		X		X	X				
Bone Turnover Markers		X	Х	X	X				
* Only for treatment									
treatment (Group A # Will occur before		luled visi	t						

Table 3: Study Visits – Group B**	9 9M	9 12M	10 18	11 24	12 30	13 42
Group D	>	12111	M	M	M	M
MD Visit		х		Х		Х
Dispense TPTD		Х	Х	Х		
Telephone Contact [#]	Х	X	Х	Х	Х	Х
Pregnancy Test		х	х	х	Х	Х
BMD by DXA		х	Х	Х	Х	Х
History & Physical		х		Х		Х
Adverse Events	х	х	Х	Х	Х	Х
Serum FSH					Х	
HR-pQCT			х		Х	Х
Central QCT					Х	
VFA by DXA		х		х		Х
Blood/Serum Archive	х	х	х	х	Х	Х
Calciotropic Hormones		х		Х		Х
Bone Turnover		х	Х	Х	Х	Х
Markers						
** Only for treatment group that started with 6 months of						
placebo injections (Group B)						

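### Table 3 mixes two clocks, so Group B has no VFA, calciotropic hormones, examination or physician visit scheduled at the end of its 24 months of teriparatide (month 30, Visit 12)

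*Combined protocol and SAP*

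**What the plan says.** The Study Design text (section 2) fixes the treatment clock. "At the 6 month timepoint, all subjects will receive TPTD", and after the 12-month visit "those initially randomized to placebo (Group B) will continue for an additional 18 months, so that subjects in both groups complete 24 months of treatment". The same section offers each woman three choices once 24 months of treatment are complete: 12 months of observation off drug, leaving the study for clinical antiresorptive treatment, or joining a new study. Section 3.A attaches that offer to a numbered visit: "At Visit 12, subjects will be presented with three options for post-TPTD follow up as described in the study design".

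"Table 3: Study Visits – Group B" has the visit and month columns "9 9M 9 12M 10 18 11 24 12 30 13 42", so Visit 12 is month 30. Its rows for MD Visit, History & Physical, VFA by DXA and Calciotropic Hormones each carry three marks, at months 12, 24 and 42. HR-pQCT is marked at months 18, 30 and 42. Central QCT and FSH are marked at month 30 only. DXA BMD, bone turnover markers, adverse events, telephone contact, pregnancy test and serum archive are also marked at month 30.

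In Table 2 (Group A), Visit 12 is month 24. VFA and calciotropic hormones are clearly marked at months 12, 24 and 36. The MD Visit and History & Physical rows contain stray characters from text extraction, but they also appear to be marked at month 24.

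**The concern.** The two schedules are meant to give each group the same drug exposure before the follow-up choice. Some Table 3 rows were shifted by 6 months to keep pace with Group B's later start, and others were not. The unshifted rows include the only routine search for vertebral fracture. Under section 3.B, spine radiographs are used when VFA is ambiguous, so without a VFA at month 30 nothing in the schedule triggers that work-up at the end of treatment.

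At stake is a comparable end-of-treatment assessment in both groups, at the visit where a woman decides whether to stay under observation or leave. A Group B woman who leaves then has her last scheduled VFA, examination and physician visit 6 months before her last dose.

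**Working it through.** **Inputs.** Group B starts teriparatide at month 6 and continues 18 months past month 12 (section 2). Group sizes are 28 and 13 (section 2). Marks are from Tables 2 and 3. Table 3 rows with all six cells filled (telephone contact, adverse events, serum archive) confirm how its cells line up with the columns.

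**Step 1: reproduce the plan's figure.** End of treatment in Group B = 12 + 18 = month 30. Exposure = 30 − 6 = 24 months, as stated. Table 3 agrees: drug is dispensed at months 12, 18 and 24 but not at month 30.

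**Step 2: convert Table 3 to time on drug.** Time on teriparatide = calendar month − 6, up to month 30.

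| Calendar month | Time on drug, Group B | HR-pQCT | Central QCT | VFA, hormones, H&P, MD visit |
|---|---|---|---|---|
| 12 | 6 months | – | – | marked |
| 18 | 12 months | marked | – | – |
| 24 | 18 months | – | – | marked |
| 30 | 24 months (end) | marked | marked | **blank** |
| 42 | 12 months off drug | marked | – | marked |

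Group A's VFA and hormone marks at months 12, 24 and 36 are 12 and 24 months on drug and 12 months off. The on-drug times are therefore 12 and 24 months in Group A and 6 and 18 months in Group B.

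**Step 3: is one clock used within a row?** No. In the four rows, the first two marks keep Group A's calendar months (12 and 24). The last moves from 36 to 42, which is 30 + 12 and so follows time on drug.

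**Step 4: does the visit numbering change the answer?** Table 3 uses the number 9 twice. If that were a slip and the columns were numbered in sequence, Visit 12 would be month 24. But section 3.A lists visits only up to 13, and section 2 ties the three choices to completing 24 months of treatment. That is month 30 whatever the number.

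**Step 5: size.** 13 / 41 = 31.7% of women. The stretch of treatment with no VFA at its end is months 18 to 24 on drug, 6 / 24 = 25% of the treatment period. Month 42 can serve only women who choose observation. The plan does not say how many will, so the number left without recovery lies between 0 and 13.

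**The case against.** The strongest defence is that efficacy imaging follows drug time while safety checks follow an annual calendar that gives both groups shared visits at months 12 and 24. No text requires the safety checks to follow drug time. This does not fully explain the table, because the same rows abandon the calendar at month 42. No rationale is given.

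Several other points stand, and they limit the consequence:

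- **Aim 3.** A reader might infer that pooling the 41 women for Aim 3 is lost. The documents do not support that. VFA and calciotropic hormones appear in no analysis in the statistical plan. The Aim 3 measures (DXA, HR-pQCT, central QCT, turnover markers) are all scheduled at month 30.
- **Distorted density.** A reader might also infer that an undetected fracture biases the month-30 spine results. A fractured vertebra can distort them, but the plan has no rule for using VFA to exclude vertebrae, so an added VFA would not change the analysis as written. The month-30 central QCT also images L1-L2 directly.
- **Hormones.** Serum is archived at every Group B visit in Table 3, and section 3.B stores PTH, 25-OHD and 1,25(OH)₂D samples frozen. If those are what the calciotropic hormone row means, the gap is largely recoverable.
- **Few events are likely.** Section 11 cites 16 women with no fractures over an average of 3 years, or 16 × 3 = 48 person-years. The rule of three gives an upper bound of 3 / 48 = 0.0625 per person-year. For 13 women over half a year (6.5 person-years) that is at most about 0.4 fractures. That series was retrospective and managed without teriparatide, so this is only a rough guide.
- **Later detection.** For women who stay under observation, the month-42 VFA could still find a deformity, though it could not date it.

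**Conclusion.** The inconsistency is real and can be read directly from the tables. Group B's end-of-treatment visit lacks four items. Two of them (VFA and calciotropic hormones) are clearly present at Group A's equivalent visit. The other two (MD visit and examination) appear to be present there, as far as the damaged Table 2 rows can be read.

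What is lost is an end-of-treatment vertebral fracture assessment, examination and physician visit in up to 13 of 41 women (32%). Those who leave at Visit 12 never reach month 42, so for them the loss is permanent. The hormone gap is minor because the serum exists. No named efficacy outcome, pooled analysis or power figure is affected. The point concerns comparable safety and fracture ascertainment and internal consistency, and it is worth correcting because the correction is cheap.

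The conclusion assumes that the extracted Table 3 marks are in their true columns, which the fully filled rows support, and that no operations manual outside these documents schedules the missing items at month 30.

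**What to change.** Reconcile Table 3 with Table 2 and with the Visit 12 text. Move Group B's month-24 VFA and calciotropic hormone marks to month 30, so that the end-of-treatment visit carries the same measurements as in Group A. The investigators should reconcile the MD Visit and History & Physical rows and state which clock they follow. Correct the repeated visit number 9 in the same edit if it is unintended.

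The month-12 marks can stay. Moving them to month 18 would complete the alignment with time on drug, but two effects need checking first. Group B's first VFA after screening would then come at month 18. Visit content would also differ further by arm at the 12-month visit, where the blind is broken and HR-pQCT already differs.

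Cost: an edit to the table, with no extra scans or assays. Group B loses the VFA and hormone sample at 18 months on drug (calendar month 24). If the month-12 mark stays, the gap between its on-treatment VFAs lengthens from 24 − 12 = 12 months to 30 − 12 = 18 months.
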